#### 9.4.5 BASELINE DESCRIPTIVE STATISTICS

Study groups will be compared on baseline characteristics, including age, race/ethnicity, gender, student group involvement, sexual orientation, and relationship status.

---

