### 2.3.3 ASSESSMENT OF POTENTIAL RISKS AND BENEFITS

The minimal risks associated with this study are reasonable given the potential impact of the project. The results of this study will provide the basis to scale-up this innovative intervention to reach a high-risk and vulnerable group, as college females are among those at the highest risk for sexual violence. This study therefore provides the opportunity to develop a low-cost/high-impact reinforcement intervention that could improve interpersonal relationships and reduce sexual violence within college campuses. As such, the available information suggests that the present clinical study has an acceptable risk-benefit ratio.

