## 4 STUDY DESIGN

### 4.1 OVERALL DESIGN

This project builds on the current momentum to address the primary prevention of sexual violence within United States institutions of higher education as well as the proliferation of web-based applications. A before-and-after quasi-experimental, mixed-method pilot design will be used to gather acceptability and safety data as well efficacy trends. Two residence halls (Alice Lloyd and Couzens) at the University of Michigan will be randomized to receive either: (1) the control arm (n=150) which will receive usual care only (all incoming students receive three programs about healthy relationships and sexual violence including Haven, Relationship Remix, and Change it Up) or (2) the usual care (n=150) described above and the web-based intervention (MKit). We will use cluster-randomization by residence hall (to minimize contamination associated with individual-level randomization of students living in the same residence hall). Following the informed consent process, students in both conditions will complete a baseline survey of xx questions. Baseline measures will include: 1) demographic data (n=12), 2) investigator developed questions on knowledge about sexual and intimate partner violence (n=20) adapted from the Texas Education Program Participant Response Form ([https://www.wcasa.org/file\\_open.php?id=787](https://www.wcasa.org/file_open.php?id=787)), 3) investigator developed questions on self-efficacy (n=15), 4) 34 questions from the Revised Intimate Partner Violence Attitude Scale (Finchman, Cuit, Braithwaite, & Pasley, 2008), 5) investigator developed questions on consensual sex (n=2), 6) 10 items from the Sexual Experiences Survey (SES) will measure past experiences with sexual violence (Koss et al., 2007) and 10 items from the Sexual Experiences Survey (SES) will measure past experiences with perpetration (Koss et al., 2007), and 7) 26 questions from the Universal Violence Prevention Screening Protocol – Adapted questions (Heron, Thompson, Jackson, & Kaslow, 2003). All of these are measures have been validated and used extensively in the United States to measure knowledge and attitudes related to gender-based violence. Following the survey, students in the Intervention group will be given the opportunity to interact with the application at their own pace, choosing which content to view in the order they prefer.

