## 6.3 MEASURES TO MINIMIZE BIAS: RANDOMIZATION AND BLINDING

Study subjects will be randomized into one of two groups: 1) Intervention (WebApp and current prevention programming on campus) or 2) Control (current prevention programming on campus only), with 150 students in each group. We will use cluster-randomization by residence hall (to minimize contamination associated with individual-level randomization of students living in the same residence hall).

This study will not involve blinding.

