#### 9.4.3 ANALYSIS OF THE SECONDARY ENDPOINT

Preliminary analyses of the survey data (knowledge, attitudes, and experiences related to sexual and intimate partner violence) will be analyzed using the Statistical Package for the Social Sciences (SPSS); all p-values will be set at  $<.05$ . Descriptive statistics will be assessed first. The baseline, 1-month post, and 5-month post-intervention tests will be examined for measures of central tendency, measures of dispersion, and frequency distribution on outcomes. Analysis of variance (ANOVA) will be utilized to determine if the scores on the baseline and follow-up tests differ significantly among the two arms. Usability and acceptability scores will be assessed among those in the intervention group.

We are not powered to assess outcome measures; however, we will look at the direction of effects for our outcome measures to allow for power calculations for future scale-up.

---

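### No arm effect adjusted for measured baseline composition is pre-specified, although one residence hall per arm cannot balance who is in each arm

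*Combined protocol and SAP*

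**What the plan says.** Allocation is by hall. Section 4.1 states: "Two residence halls (Alice Lloyd and Couzens) at the University of Michigan will be randomized to receive either" usual care alone or usual care plus MKit. Section 6.3 adds "We will use cluster-randomization by residence hall (to minimize contamination associated with individual-level randomization of students living in the same residence hall"), "with 150 students in each group". No matching, stratification or restriction is described. The schedule of activities (1.3) places randomization before recruitment. Under section 5.5, interested students then receive a palm card whose link differs by arm.

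The arm comparison is given in section 9.4.3, and in the same terms in 9.4.1: "Analysis of variance (ANOVA) will be utilized to determine if the scores on the baseline and follow-up tests differ significantly among the two arms". No covariate, change score or group-by-time term is named. Section 9.4.9 adds only that the direction of effects will be explored, to support power calculations for a later study.

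The baseline characteristics appear in two places. Section 9.4.5 says: "Study groups will be compared on baseline characteristics, including age, race/ethnicity, gender, student group involvement, sexual orientation, and relationship status". Section 9.4.7 plans subgroup analyses of the primary and secondary endpoints by the same list without age. Neither section says what follows for the overall arm comparison if the groups differ.

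**The concern.** With two halls, randomization decides only which hall gets MKit. It does not mix students between the arms. Differences in who lives in each hall pass straight into the comparison, and so do differences in who volunteers once the invitations differ by arm. If gender or relationship status is related to an outcome and its mix differs between the halls, the crude arm difference contains a component that has nothing to do with MKit.

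The protocol gives one such relation itself. Section 2.3.3 says that "college females are among those at the highest risk for sexual violence", and sexual victimization is a secondary endpoint. At stake is the sign and size of the arm differences that are meant to inform the next trial. More students from the same two halls would not remove this component. Adjustment for characteristics already collected could largely remove the measured part of it.

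**Working it through.** The plan has no power or precision figure to reproduce. Section 9.2 says the sample size was chosen for feasibility.

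**Inputs from the documents:** 150 students per arm; one hall per arm; test level .05 (taken as two-sided).

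**Assumptions, since the documents give no values:** gender gap in a score 0.2 to 0.8 SD; difference in gender share between halls 5 to 30 points; no dropout; at first no hall effect; a crude comparison of follow-up scores.

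**Precision.** SE of the arm difference = sqrt(2/150) = 0.115 SD, so the 95% half-width is 1.96 × 0.1155 = 0.226 SD.

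**Balance under individual randomization, for contrast.** For a characteristic held by half the students, the SD of the difference in share is sqrt(0.25 × 2/150) = 0.058. The 95% range is about ±11 points. With one hall per arm this bound does not apply.

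**Composition shift** = difference in share × gap. With no true effect, the probability that the estimated sign follows composition is Φ(shift/SE). The nominal 5% test rejects with probability 1 − Φ(1.96 − shift/SE) + Φ(−1.96 − shift/SE).

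| Gap (SD) | Share difference | Shift (SD) | Sign follows composition | Rejection rate |
|---|---|---|---|---|
| 0.2 | 5 points | 0.01 | 0.535 | 5.1% |
| 0.2 | 10 points | 0.02 | 0.569 | 5.3% |
| 0.5 | 10 points | 0.05 | 0.667 | 7.2% |
| 0.5 | 20 points | 0.10 | 0.807 | 13.9% |
| 0.8 | 30 points | 0.24 | 0.981 | 54.7% |

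**With a true benefit of 0.10 SD.** The right sign appears with probability Φ(0.10/0.1155) = 0.81. If a composition shift of 0.10 SD runs against it, this falls to Φ(0) = 0.50.

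**A yes/no outcome.** With assumed rates of 10% in women and 3% in men, a 20-point difference in share gives 0.20 × 7 = 1.4 percentage points with no MKit effect.

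**Effect of adjustment** (simulation, 20,000 runs, gap 0.5 SD, 20 points, no true effect, no hall effect). Unadjusted: mean estimate 0.10 SD, rejection 12.7%. With gender as covariate: mean 0.00 SD, rejection 5.1%.

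**What adjustment leaves.** Let ICC be the assumed share of variance between halls, so that SE = sqrt(2 × (ICC + (1 − ICC)/150)).
- ICC 0.01: SE = sqrt(2 × (0.01 + 0.0066)) = 0.18 SD. A perfectly adjusted 0.10 SD benefit has the right sign about 71% of the time.
- ICC 0.05: SE = sqrt(2 × (0.05 + 0.0063)) = 0.34 SD, and about 62%.
- In the simulation with no true effect, the gender-adjusted test still rejected in 21%, 32% and 50% of runs at ICC 0.01, 0.02 and 0.05.

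**If the baseline score is used.** A stable gap shrinks by the factor (1 − slope of follow-up on baseline within gender). With an assumed slope of 0.7, the shift of 0.10 SD becomes 0.10 × 0.3 = 0.03 SD.

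**The case against.** A reader might infer that the plan ignores gender and the other characteristics, or does nothing once an imbalance is seen. The documents do not support that. Section 9.4.7 analyzes endpoints by five of the six characteristics, and an arm comparison within gender would be free of gender-composition bias. What remains is narrower: subgroup results taken one characteristic at a time do not give an adjusted overall arm effect.

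A reader might also infer that the protocol says gender drives every outcome. Section 2.3.3 speaks only of the risk of sexual violence. It says nothing of knowledge, self-efficacy, attitudes or perpetration. A link between relationship status and exposure to partner violence is plausible, but the documents do not state it.

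Third, the ANOVA need not be a crude comparison of follow-up scores. Section 4.1 calls the design "A before-and-after quasi-experimental, mixed-method pilot design will be used to gather acceptability and safety data as well efficacy trends", and a change or group-by-time analysis would cancel a stable difference in level. The text names no such term, however. Even that form would leave gender differences in change, including different rates of new victimization during follow-up.

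Finally, hall and arm are fully confounded whatever is adjusted for, and the comparison is secondary and repeatedly declared unpowered. Both points stand, and they limit the importance of the gap. They do not justify leaving it: low power concerns random error, while a composition shift is systematic and its measured part can be removed.

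**Conclusion.** The concern holds in a limited form. The plan compares the arms by an ANOVA of unspecified form with no named covariate, in a design that cannot balance composition, and it pre-specifies no adjusted overall arm effect.

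The size depends on values that the documents do not give. Over the assumed ranges the shift runs from 0.01 SD, which hardly matters, to 0.24 SD, about twice the standard error. The middle case of 0.10 SD is close to one standard error. The fall from 81% to 50% in the chance of a right sign comes from setting the shift equal and opposite to the chosen effect, with no hall effect. It is an illustration and not a forecast.

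It would also be too strong to infer that adjustment makes the arm comparison trustworthy. It removes measured composition differences only. The primary endpoints in section 9.4.2, which are scores in the intervention group and interviews, are not affected. This is a cheap improvement of modest importance.

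**What to change.** In sections 9.4.3 and 9.4.9:

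- State the form of the analysis. Pre-specify a linear model at 1 and 5 months (logistic for yes/no experience outcomes) with arm, the baseline score where there is one, gender, relationship status and a short fixed list of the other characteristics in 9.4.5.
- Use covariate values from the baseline survey. The schedule repeats demographics at follow-up, and relationship status may change after allocation.
- For rare events, reduce the covariates to gender and relationship status.
- Report the adjusted difference beside the crude one, each with a 95% interval.
- State that adjustment removes measured composition differences but not hall effects, which are fully confounded with arm, and that the intervals do not include hall effects.

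Fixing the list now also prevents covariates being chosen after the baseline table has been seen.

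The cost is a few lines of text, an extra table column, slightly more analysis and a small loss of degrees of freedom. The demographics and the scales are already scheduled at baseline, so no further data or participants are needed. The baseline-score term requires each student's surveys to be linked, which section 4.4 already presupposes by defining completion over all three surveys.

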#### 9.4.6 PLANNED INTERIM ANALYSES

Not Applicable

---

#### 9.4.7 SUB-GROUP ANALYSES

Primary and secondary endpoints will be analyzed based on gender, race/ethnicity, student group involvement, sexual orientation, and relationship status.

---

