### 5.5 STRATEGIES FOR RECRUITMENT AND RETENTION

Students from the target sample, first-year University of Michigan college students, will be recruited for the study. Two residence halls (Alice Lloyd and Couzens) at the University of Michigan will be randomized to receive either: (1) the control arm ( $n=150$ ) which will receive usual care only (all incoming students receive three programs about healthy relationships and sexual violence including Haven, Relationship Remix, and Change it Up) or (2) the usual care ( $n=150$ ) described above and the web-based intervention (MKit). We will use cluster-randomization by residence hall (to minimize contamination associated with individual-level randomization of students living in the same residence hall). At the end of the Relationship

Remix program, a brief announcement will be made about the opportunity to participate in a research study about healthy relationships and palm cards will be distributed (see recruitment materials). We will recruit specifically from Relationship Remix to ensure that all experimental and control subjects receive the same primary prevention programming currently in place on campus. Interested students will receive a palm card with a link to either the MKit web-based application (Intervention) with an access code to sign-up for the website, or a link to the baseline consent and Qualtrics survey (Control) without access to the web-based application. At the end of the study, students from each condition will be invited to participate in an in-person semi-structured interview. Students will receive the invitation to participate in the semi-structured interview on the final page of their 5-month follow-up survey. Students who opt to share their email address with the study team at that time will be contacted to set-up an in-person interview based on user status for the intervention (consistent user of MKit, frequent user of MKit, minimal user of MKit) and a diverse group based on gender, race/ethnicity, and age for the control group. Semi-structured interviews will be conducted with participants from both the Control group (n=10) and the Intervention group (n=15).

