### 9.3 POPULATIONS FOR ANALYSES

All data collected through the pilot study process will be utilized for the analyses related to feasibility, usability, and acceptability. The data collected from the semi-structured interview subjects will be utilized to analyze the safety of the application and the willingness of participants to use the application.

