### 9.4 STATISTICAL ANALYSES

#### 9.4.1 GENERAL APPROACH

The survey data will be analyzed using the Statistical Package for the Social Sciences (SPSS); all p-values will be set at  $<.05$ . Descriptive statistics will be assessed first. The baseline, 1-month post, and 5-month post-intervention tests will be examined for measures of central tendency, measures of dispersion, and frequency distribution on outcomes. Analysis of variance (ANOVA) will be utilized to determine if the scores on the baseline and follow-up tests differ significantly among the two arms. Usability and acceptability scores will be assessed among those in the intervention group.

We are not powered to assess outcome measures (sexual violence experiences/behaviors, rape myth acceptance, or sexual relationship power); however, we will look at the direction of effects for our outcome measures to allow for power calculations for a future R-Level submission. The results of this project will establish the safety and usability of this adapted web-based application for future scale-up.

For the semi-structured interviews, all audiotapes will be transcribed verbatim. Data analyses will be conducted using an iterative process and the constant comparative method of analysis (Glaser, 1992). Member checking will contribute to credibility through validation of the research findings by participants. A codebook will be developed after repeated high-level reading of the transcripts by the study team. Data will be coded and grouped into categories to facilitate abstraction and concept analysis.

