#### 9.4.2 ANALYSIS OF THE PRIMARY ENDPOINT

The safety of MKit and the willingness of participants to use it will be assessed through post-intervention semi-structured interviews, conducted with 25 participants including 15 participants from the intervention group and 10 participants from the control group. The usability for the WebApp will be assessed at two time points (1-month and 5-months) using the 10-item System Usability Scale (Brooke, 1996). The acceptability of the WebApp will be assessed at two time points (1-month and 5-months) using an investigator created 5-item acceptability scale. Usability and acceptability scores will be assessed among those in the intervention group.

For the semi-structured interviews, all audiotapes will be transcribed verbatim. Data analyses will be conducted using an iterative process and the constant comparative method of analysis (Glaser, 1992). Member checking will contribute to credibility through validation of the research findings by participants. A codebook will be developed after repeated high-level reading of the

transcripts by the study team. Data will be coded and grouped into categories to facilitate abstraction and concept analysis. An audit trail will be established to allow others to follow the decisions made by the research team (Sandelowski & Barroso, 2003). The results of the semi-structured interviews will be used to: 1) update the content of MKit, as needed; 2) assess the safety of MKit; 3) assess the usability and willingness to use MKit; and 4) assess the acceptability of MKit.

---

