#### 9.4.4 SAFETY ANALYSES

The safety of MKit will be assessed through post-intervention semi-structured interviews, conducted with 25 participants including 15 participants from the intervention group and 10 participants from the control group.

---

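### Section 9.4.7 plans subgroup analyses of every endpoint by five factors with no method, multiplicity control or exploratory label, and 15 app-exposed interviewees cannot support subgroup conclusions on safety or willingness

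*Combined protocol and SAP*

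**What the plan says.** Section 9.4.7 is a single sentence: "Primary and secondary endpoints will be analyzed based on gender, race/ethnicity, student group involvement, sexual orientation, and relationship status". It names no test, factor levels, minimum group size or adjustment for multiple testing, and it does not say which time point's value places a student in a subgroup.

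The rules that an analyst could carry into it are elsewhere:

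- **Survey data.** Section 9.4.1, which sets the threshold at <.05: "The survey data will be analyzed using the Statistical Package for the Social Sciences (SPSS); all p-values will be set at". Sections 9.4.1 and 9.4.3 then use ANOVA to judge whether the two arms' scores differ significantly.
- **Power.** Section 9.4.3: "We are not powered to assess outcome measures". The same sentence says that the direction of effects will be examined to inform later power calculations.
- **Primary scales.** Section 9.4.2: "Usability and acceptability scores will be assessed among those in the intervention group".
- **Interview endpoints.** Section 9.3, on safety and on willingness to use the app: "The data collected from the semi-structured interview subjects will be utilized to analyze the safety of the application and the willingness of participants". Section 9.4.4 says that the interviews are "conducted with 25 participants including 15 participants from the intervention group and 10 participants from the control group".
- **Who is interviewed.** Under section 5.5 the control group is recruited "without access to the web-based application". Intervention interviewees are picked "based on user status for the intervention (consistent user of MKit, frequent user of MKit, minimal user of MKit"; a spread of gender, race/ethnicity and age is asked for only among the controls.

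**The concern.** The sentence commits the study to subgroup analysis of every primary and secondary endpoint, and it raises a different problem for each kind of endpoint.

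For the survey endpoints, 9.4.7 leaves the general .05 rule as the only one available. Applied across many measures, two follow-ups and five factors without adjustment, it is likely to produce significant subgroup results when nothing is going on. The study exists partly to inform a larger trial, so a chance finding for one gender, race/ethnicity or orientation group could steer the design of that trial.

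For safety and willingness, alpha is not the issue, because these are qualitative. The issue is numbers: only the intervention interviewees have used MKit, and they are not sampled on any of the five factors. A statement that the app is safe for, or welcome in, a particular group could rest on one or two people, or on none.

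**Working it through.** The plan gives no power or error-rate figure for subgroups, so there is none to reproduce.

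**Inputs from the documents**

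- Secondary measures (section 3): knowledge, self-efficacy, attitudes, consensual activity, sexual victimization, sexual perpetration and the violence screening questions = 7. Retention is a further endpoint.
- Primary scales (section 9.4.2): usability and acceptability = 2, intervention arm only.
- Post-baseline time points (section 4.1): 1 and 5 months = 2.
- Subgroup factors (section 9.4.7): 5.
- Per-test threshold (sections 9.4.1 and 9.4.3): .05.
- Interviewees (section 9.4.4): 25, of whom 25 - 10 = 15 had the app.

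**Assumption.** The plan does not define the subgroup tests. I take one test per measure, follow-up and factor, each holding its 5% level.

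**Survey endpoints, no true effects**

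Number of tests m = measures x 2 x 5. Expected false positives = 0.05 x m. If the tests are independent, P(at least one) = 1 - 0.95^m.

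| Set | m | Expected | P, independent | P, correlated |
|---|---|---|---|---|
| 7 secondary measures | 70 | 3.5 | 97.2% | 75-95% |
| 2 primary scales | 20 | 1.0 | 64.2% | 47-60% |
| All 9 measures | 90 | 4.5 | 99.0% | 80-97% |

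The last column comes from simulating correlated two-sided z-tests (40,000 draws per setting). The correlations are assumed, not taken from the documents: 0.3 to 0.7 between measures, 0.5 to 0.8 between time points and 0 to 0.3 between factors. For the 70 secondary tests the four settings gave 94.7%, 93.0%, 87.8% and 74.8%. Correlation lowers the chance of at least one false positive but leaves the expected number unchanged.

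The count depends on how the section is read. Comparing the arms separately within two levels of each factor would give 7 x 2 x 10 = 140 tests for the secondary measures, with 7.0 false positives expected. Using one follow-up only would give 7 x 1 x 5 = 35 tests, with 1.75 expected and 1 - 0.95^35 = 83.4% if independent.

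**Interview endpoints**

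For a factor level with share p of students, and treating the 15 as a random draw with respect to that factor (an assumption):

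P(no interviewee) = (1 - p)^15, and P(at most one) = (1 - p)^15 + 15p(1 - p)^14.

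| Assumed share p | P(none) | P(at most one) |
|---|---|---|
| 5% | 46.3% | 82.9% |
| 10% | 20.6% | 54.9% |
| 20% | 3.5% | 16.7% |

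The shares are illustrative, since the documents give no composition of the student body.

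**The case against.** The strongest reply is that this is a declared pilot. Section 9.1 frames the secondary aim as exploring preliminary differences, section 9.4.9 labels its analyses exploratory, and sections 9.4.1 and 9.4.3 disclaim power and point to the direction of effects. No sentence promises a subgroup claim. The number of tests is also a construction, because the plan lists none.

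Much of this stands, and it keeps the point minor. It does not remove it. A disclaimer about power concerns missed effects, not false positives. The .05 threshold and the significance wording sit in the same sections as the disclaimer. Section 9.4.7 carries no exploratory label, although 9.4.9 does.

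It is also fair to say that MKit was adapted for a population diverse in race, ethnicity and gender/sexual identity (section 1.1), so looking at interview themes by these factors is relevant. Descriptive use is reasonable; a subgroup conclusion is not.

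The documents do not support three stronger readings that a reader might infer:

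- *Every endpoint is tested at .05.* Section 9.4.7 sets no threshold, the .05 rule covers survey data, and safety and willingness have no significance test.
- *False positives are all but certain.* That needs near-independence among many tests. It does not hold across the range of correlations examined, nor for the two primary scales alone.
- *The interviews yield a subgroup harm rate that could be bounded.* They assess perceived safety and reactions (sections 1.3 and 4.1), and adverse events are recorded separately throughout participation (section 8.3.4).

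**Conclusion.** The concern holds as a minor point about section 9.4.7. Followed as written, with the only survey rule that the plan supplies, it would yield unadjusted subgroup significance results. For the seven secondary measures, 3.5 false positives would be expected if there are no true effects, with about a 75-97% chance of at least one. That range runs from the strongest assumed correlations to independence. It rests on one test per measure, follow-up and factor, which the plan does not specify.

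For safety and willingness, 15 exposed interviewees chosen by level of use cannot support conclusions by gender, race/ethnicity, student group involvement, sexual orientation or relationship status. That conclusion depends on neither alpha nor the test count; only the chances of empty or near-empty levels use assumed shares.

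The point does not affect the main descriptive analysis of usability and acceptability in the intervention arm.

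**What to change.** Reword section 9.4.7:

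- Label the subgroup analyses exploratory.
- For survey endpoints, define each subgroup by its baseline value. Section 1.3 collects demographics again at 1 and 5 months, and relationship status or group involvement can change after exposure.
- Report estimates with 95% confidence intervals and make no significance statements.
- Where the arms are compared, give the arm-by-factor interaction estimate instead of p-values within subgroups. State that, with one residence hall per arm (section 4.1), this cannot be separated from a hall-by-factor difference, and that its interval does not reflect hall-level variation.
- For safety and willingness, use the five factors only to describe the interviewees and their themes, and draw no subgroup conclusion.

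This still serves the stated interest in direction of effects. The cost is a change of wording in one section and the loss of subgroup p-values. No extra data are needed.
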